The New CDC-definitions for surveillance of surgical site infections (1992) take into account 3 classes of surgical site infections (SSI): superficial incisional SSI, deep incisional SSI, and organ/space SSI. The most prevalent host-related risk factors for development of SSI are advanced age, morbid obesity, disease severity, an ASA score > 2, prolonged preoperative hospital stay, and infection at distal sites. Microbial contamination of the surgical site occurs mainly during the surgical intervention.

Although exogenous contamination from the surgical suite may be of concern, especially in clean operations, most surgical site infections are caused by microorganisms of the patient's own skin flora. SSI rates vary according to the type and duration of the surgical procedure. Proper surgical technique is probably the most important factor in the prevention of SSI. Modification of patient risk factors should be attempted whenever possible through use of adequate protocols for antimicrobial prophylaxis with antibiotics should be followed. Routine surveillance of surgical site infections is beneficial for SSI prevention and early detection. Additional prevention aimed at decreasing number of microorganisms on patient's skin pre-operatively may decrease rates of SSI. Prior studies have reported daily use of 2% chlorhexidine gluconate (CHG) cloths has decreased rates of nosocomial bloodstream infections in those with central line catheters. Another study reported decreasing SSIs up to 50% when nursing staff instituted utilization of CHG cloths pre-op and daily post-op cleansing in-hospital. However, use of CHG cloths pre-operatively has not been routinely instituted. Many hospitals and service lines do not have a protocol for their use. Therefore study of such a population may prove worthy, as currently VUMC neuro-spine patients do not routinely utilize preoperative skin cleansing with CHG cloths.

This study proposes a randomized, controlled trial of neuro-spine patients of 2% chlorhexidine gluconate skin preparation cloths for the prevention of post op surgical site infections in spine patients.

2. Hypothesis:

Use of CHG cloths the night before and morning of surgery (neckline to toes) will affect (decrease rates) of SSI compared to patients who receive routine standard of care (soap and water pre-op, day of surgery and daily post-operative).

3. Study Objectives:

- Randomize consented patients pre-operative to either study group (of 2% chlorhexidine gluconate cloths the night before and morning of surgery) or control (standard of care cleansing with soap and water) with follow-up through discharge for evaluation of SSI
- Evaluation for SSI development at 6 week (+/-) 1 week post-op visit.

- Measure change in skin flora by comparing skin swab cultures of those using the cloths and those who do not on day of surgery, post-op day 4 or hospital discharge and postop day 30

4. Methods:

Pre-operatively patients scheduled for neurosurgical spine cases will be evaluated and approached for interest, if consenting process completed, patients will be randomized to one of 2 arms in 1:1 through a block randomization table.

Those enrolled into the study arm will receive the CHG cloths and instructions for use from research personal. Those randomized to the control arm will receive standard of care skin cleansing by nursing staff.

All subjects who have signed consent will have a skin swab culture taken the day of screening and prior to cleansing with Chlorhexidine gluconate wipes close to the intended incision line. We will also obtain skin swab cultures at site of incision preoperatively on the day of surgery, post-op day 4 or time of discharge (which ever comes first) and at the 30 day follow up.

Both groups will be evaluated daily by study personnel for the development of SSI until post-op day 4 or hospital discharge whichever one comes first.. Additional evaluations will take place at the 30 day (+/- 7 days) post-op visit. Blinded evaluators utilizing the CDC guideline will grade the incision line for presence of SSI. Measured change in skin flora will be performed by comparing skin swab cultures of intervention group versus standard of care group and individual changes pre and post operatively.

5. Patient Population:

Neurosurgical spine patients at Vanderbilt University Medical Center

6. Enrollment:

170 patients will be enrolled.

7. Inclusion/Exclusion Criteria:

Inclusion Criteria

Patients scheduled for a neuro-spine procedure and have 2 of the following risk factors:
Diabetic OR BMI>30 OR ASA_≥2 OR pre-operatively hospitalized OR >60 years old OR chronic steroids/immunosuppressive medications OR prior history of SSI

Exclusion Criteria

- 1) Unable to consent
- 2) Non English speaking
- 3) Known allergy to any of the ingredients contained in SAGE chlorhexidine gluconate cloths
- 4) Current infection or history of spine infections.
- 5) Patients with tumors or intradural spinal pathology.

8. Data Collection:

Data regarding demographics, health history and status, surgical course and hospitalization will be collected and entered into an electronic database. Patient data will be de-identified once entered into the database. Shared data will always be de-identified and accessed through Redcap, a secure web-based system.

9. Reporting of Adverse Events or Unanticipated Problems involving Risk to Participants or Others:

Events determined by the Principal Investigator (PI) to be unanticipated problems involving risks to subjects will be reported by the PI or sub-investigator to the IRB within 10 working days of the Investigator's knowledge of the problem.

10. Statistical Plan:

We are planning a study of independent cases and controls with 1 control(s) per case. Prior data indicate the rate of infection in the control group (those with risk factors, including superficial SSI) is 0.5, then just 150 evaluable subjects are needed to detect a 50% or greater reduction, with 80% power. We can also design a statistical analysis plan that uses the grade of SSI instead of binary yes/no to indicate presence of SSI. This should increase the power as well, for instance, if the SAGE cloths reduce the severity of (but does not completely prevent) infection in some patients.

11. Privacy/Confidentiality Issues

All reasonable efforts will be made to keep a patient's protected health information (PHI) private and confidential. There will be limited access to electronic medical records and de-identification of all records. Federal privacy guidelines will be followed when using or sharing any protected health information.

Data will be stored in Redcap, a secure web-based database conforming to the latest Vanderbilt IS security policies. Data from the study will be reported only in the aggregate.

Under the supervision of each site's PI, Vanderbilt research team members will view research records and collect data as identified above. Medical records will be stored separately from the data and remain on-site. All de-identified data-points will be entered directly into Redcap, a secure web-based database. No identified information will leave the site.

All study staff have completed employee education regarding patient confidentiality and have completed Human Subjects protection education (CITI course) as specified by the Vanderbilt IRB.

Through these interventions, we expect risks to privacy to be minimized.

12. Follow-up and Record Retention

Research Records will be retained by the Nursing Research Office for a period of six (6) years after the submission of the final report and close-out procedures on the research project for which the Research Records were prepared.

The retention of the original Research Records shall be the responsibility of the Nursing Research Office.

Study Schema

Procedure	screening	Day of surgery	POD 1	POD 2	POD 3	POD4 or discharge	6 weeks ± 1 week follow up visit
Written informed consent	X						
Medical history	X						
Urine pregnancy test		X					
BMI	X						
Vital signs (HR, RR, BP, T)	X	X	X	X	X	X	X
Randomization	X						
SAGE cloths for treatment arm ¹	X	X					
Standard of care; soap and water for control arm	X	X	X	X	X	X	
Skin culture	X	X				X	X
Post surgical assessment			X	X	X	X	X
Blinded assessor to evaluate for s/sx of SSI							X
Assess for adverse events	X	X	X	X	X	X	X
medications	X	X	X	X	X	X	X

¹Supplies will be given to participants at screening visit. Application will be done by the participant on the evening before surgery.

References

2. Balderston RA, Blumberg K (1991) Infection in spine surgery. In: Balderston RA, An HS (eds) *Complications in spinal surgery*. WB Saunders, Philadelphia, pp 157–168
4. Keller RB, Pappas AM (1972) Infection after spinal fusion using internal fixation instrumentation. *Orthop Clin North Am* 3:99–111PubMed
8. West JL 3rd, Ogilvie JW, Bradford DS (1991) Complications of the variable screw plate pedicle screw fixation. *Spine* 16:576–579CrossRefPubMed

35. Tsiodras S, Falagas ME (2006) Clinical assessment and medical treatment of spine infections. *Clin Orthop Relat Res* 444:38–50CrossRefPubMed

36. Pull ter Gunne AF, Cohen DB (2009) Incidence, prevalence and analysis of risk factors for surgical site infection following adult spinal surgery. *Spine* (in press)

38. Eiselt, Debra (2009) Presurgical Skin Preparation With a Novel 2% Chlorhexidine Gluconate Cloth Reduces Rates of Surgical Site Infection in Orthopaedic Surgical Patients Orthopaedic Nursing: May/June 2009 - Volume 28 - Issue 3 - p 141–145 doi: 10.1097/NOR.0b013e3181a469db

Table of Contents:

- 1. Background and Significance**
- 2. Hypothesis**
- 3. Study Objectives**
- 4. Methods**
- 5. Patient Population**
- 6. Enrollment**
- 7. Inclusion/Exclusion Criteria**
- 8. Data Collection**
- 9. Reporting of Adverse Events or Unanticipated Problems involving Risk to Participants or Others:**
- 10. Statistical Plan**
- 11. Privacy/Confidentiality Issues**
- 12. Follow-up and Record Retention**

1. Background and Significance:

Surgical site infection (SSI) following spinal surgery is a frequent complication and results in higher morbidity, mortality and healthcare costs. SSI following adult spinal surgery is a frequent complication that has been reported to occur in 0.7–12.0% of patients and result in higher postoperative morbidity, mortality and health care costs. Vanderbilt University Medical Center SSI rate is 7%. Treatment for SSI can be challenging often requiring revision surgery, long-term antibiotics, and prolonged hospitalization. The accurate identification of risk factors is thus important in the development of strategies to prevent these potentially devastating infections.

The New CDC-definitions for surveillance of surgical site infections (1992) take into account 3 classes of surgical site infections (SSI): superficial incisional SSI, deep incisional SSI, and organ/space SSI. The most prevalent host-related risk factors for development of SSI are advanced age, morbid obesity, disease severity, an ASA score > 2, prolonged preoperative hospital stay, and infection at distal sites. Microbial contamination of the surgical site occurs mainly during the surgical intervention.

Although exogenous contamination from the surgical suite may be of concern, especially in clean operations, most surgical site infections are caused by microorganisms of the patient's own skin flora. SSI rates vary according to the type and duration of the surgical procedure. Proper surgical technique is probably the most important factor in the prevention of SSI. Modification of patient risk factors should be attempted whenever possible through use of adequate protocols for antimicrobial prophylaxis with antibiotics should be followed. Routine surveillance of surgical site infections is beneficial for SSI prevention and early detection. Additional prevention aimed at decreasing number of microorganisms on patient's skin pre-operatively may decrease rates of SSI. Prior studies have reported daily use of 2% chlorhexidine gluconate (CHG) cloths has decreased rates of nosocomial bloodstream infections in those with central line catheters. Another study reported decreasing SSIs up to 50% when nursing staff instituted utilization of CHG cloths pre-op and daily post-op cleansing in-hospital. However, use of CHG cloths pre-operatively has not been routinely instituted. Many hospitals and service lines do not have a protocol for their use. Therefore study of such a population may prove worthy, as currently VUMC neuro-spine patients do not routinely utilize preoperative skin cleansing with CHG cloths.

This study proposes a randomized, controlled trial of neuro-spine patients of 2% chlorhexidine gluconate skin preparation cloths for the prevention of post op surgical site infections in spine patients.

2. Hypothesis:

Use of CHG cloths the night before and morning of surgery (neckline to toes) will affect (decrease rates) of SSI compared to patients who receive routine standard of care (soap and water pre-op, day of surgery and daily post-operative).

3. Study Objectives:

- Randomize consented patients pre-operative to either study group (of 2% chlorhexidine gluconate cloths the night before and morning of surgery) or control (standard of care cleansing with soap and water) with follow-up through discharge for evaluation of SSI
- Evaluation for SSI development at 6 week (+/-) 1 week post-op visit.

- Measure change in skin flora by comparing skin swab cultures of those using the cloths and those who do not on day of surgery, post-op day 4 or hospital discharge and postop day 30

4. Methods:

Pre-operatively patients scheduled for neurosurgical spine cases will be evaluated and approached for interest, if consenting process completed, patients will be randomized to one of 2 arms in 1:1 through a block randomization table.

Those enrolled into the study arm will receive the CHG cloths and instructions for use from research personal. Those randomized to the control arm will receive standard of care skin cleansing by nursing staff.

All subjects who have signed consent will have a skin swab culture taken the day of screening and prior to cleansing with Chlorhexidine gluconate wipes close to the intended incision line. We will also obtain skin swab cultures at site of incision preoperatively on the day of surgery, post-op day 4 or time of discharge (which ever comes first) and at the 30 day follow up.

Both groups will be evaluated daily by study personnel for the development of SSI until post-op day 4 or hospital discharge whichever one comes first.. Additional evaluations will take place at the 30 day (+/- 7 days) post-op visit. Blinded evaluators utilizing the CDC guideline will grade the incision line for presence of SSI. Measured change in skin flora will be performed by comparing skin swab cultures of intervention group versus standard of care group and individual changes pre and post operatively.

5. Patient Population:

Neurosurgical spine patients at Vanderbilt University Medical Center

6. Enrollment:

170 patients will be enrolled.

7. Inclusion/Exclusion Criteria:

Inclusion Criteria

Patients scheduled for a neuro-spine procedure and have 2 of the following risk factors:
Diabetic OR BMI>30 OR ASA_≥2 OR pre-operatively hospitalized OR >60 years old OR chronic steroids/immunosuppressive medications OR prior history of SSI

Exclusion Criteria

- 1) Unable to consent
- 2) Non English speaking
- 3) Known allergy to any of the ingredients contained in SAGE chlorhexidine gluconate cloths
- 4) Current infection or history of spine infections.
- 5) Patients with tumors or intradural spinal pathology.

8. Data Collection:

Data regarding demographics, health history and status, surgical course and hospitalization will be collected and entered into an electronic database. Patient data will be de-identified once entered into the database. Shared data will always be de-identified and accessed through Redcap, a secure web-based system.

9. Reporting of Adverse Events or Unanticipated Problems involving Risk to Participants or Others:

Events determined by the Principal Investigator (PI) to be unanticipated problems involving risks to subjects will be reported by the PI or sub-investigator to the IRB within 10 working days of the Investigator's knowledge of the problem.

10. Statistical Plan:

We are planning a study of independent cases and controls with 1 control(s) per case. Prior data indicate the rate of infection in the control group (those with risk factors, including superficial SSI) is 0.5, then just 150 evaluable subjects are needed to detect a 50% or greater reduction, with 80% power. We can also design a statistical analysis plan that uses the grade of SSI instead of binary yes/no to indicate presence of SSI. This should increase the power as well, for instance, if the SAGE cloths reduce the severity of (but does not completely prevent) infection in some patients.

11. Privacy/Confidentiality Issues

All reasonable efforts will be made to keep a patient's protected health information (PHI) private and confidential. There will be limited access to electronic medical records and de-identification of all records. Federal privacy guidelines will be followed when using or sharing any protected health information.

Data will be stored in Redcap, a secure web-based database conforming to the latest Vanderbilt IS security policies. Data from the study will be reported only in the aggregate.

Under the supervision of each site's PI, Vanderbilt research team members will view research records and collect data as identified above. Medical records will be stored separately from the data and remain on-site. All de-identified data-points will be entered directly into Redcap, a secure web-based database. No identified information will leave the site.

All study staff have completed employee education regarding patient confidentiality and have completed Human Subjects protection education (CITI course) as specified by the Vanderbilt IRB.

Through these interventions, we expect risks to privacy to be minimized.

12. Follow-up and Record Retention

Research Records will be retained by the Nursing Research Office for a period of six (6) years after the submission of the final report and close-out procedures on the research project for which the Research Records were prepared.

The retention of the original Research Records shall be the responsibility of the Nursing Research Office.

Study Schema

Procedure	screening	Day of surgery	POD 1	POD 2	POD 3	POD4 or discharge	6 weeks ± 1 week follow up visit
Written informed consent	X						
Medical history	X						
Urine pregnancy test		X					
BMI	X						
Vital signs (HR, RR, BP, T)	X	X	X	X	X	X	X
Randomization	X						
SAGE cloths for treatment arm ¹	X	X					
Standard of care; soap and water for control arm	X	X	X	X	X	X	
Skin culture	X	X				X	X
Post surgical assessment			X	X	X	X	X
Blinded assessor to evaluate for s/sx of SSI							X
Assess for adverse events	X	X	X	X	X	X	X
medications	X	X	X	X	X	X	X

¹Supplies will be given to participants at screening visit. Application will be done by the participant on the evening before surgery.

References

2. Balderston RA, Blumberg K (1991) Infection in spine surgery. In: Balderston RA, An HS (eds) *Complications in spinal surgery*. WB Saunders, Philadelphia, pp 157–168
4. Keller RB, Pappas AM (1972) Infection after spinal fusion using internal fixation instrumentation. *Orthop Clin North Am* 3:99–111PubMed
8. West JL 3rd, Ogilvie JW, Bradford DS (1991) Complications of the variable screw plate pedicle screw fixation. *Spine* 16:576–579CrossRefPubMed

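### Skin flora: name the screening swab as baseline and adjust the arm comparison for it (minor, nearly free); 'pre' is currently open between two preoperative swabs

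*Combined protocol and SAP*

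**What the plan says.** Section 3 makes change in skin flora an objective, comparing those who use the cloths with those who do not "on day of surgery, post-op day 4 or hospital discharge and postop day 30". Section 4 gives the whole analysis in one sentence: "comparing skin swab cultures of intervention group versus standard of care group and individual changes pre and post operatively". Section 10 (Statistical Plan) deals only with surgical site infection and gives no flora model, scale, baseline or main time point.

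Four swabs are planned. Every consented subject has a "skin swab culture taken the day of screening and prior to cleansing with Chlorhexidine gluconate wipes close to the intended incision line". Section 4 then adds "skin swab cultures at site of incision preoperatively on the day of surgery, post-op day 4 or time of discharge (which ever comes first", and a last one at the 30-day follow-up.

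On the timing of the cloths, footnote 1 of the Study Schema says "Application will be done by the participant on the evening before surgery". Section 2 has them used both the night before and on the morning of surgery.

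The schema row "Standard of care; soap and water for control arm" is ticked in the screening column, the same column as randomization and the first skin culture.

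**The concern.** Both the screening and the day-of-surgery swab fit the word 'preoperative', and they are not interchangeable. The screening swab is the only one documented as taken before CHG cleansing. On either account of cloth timing, the day-of-surgery swab in the CHG arm follows at least one planned application. It is therefore a post-randomization measurement that may already carry the treatment effect. An arm comparison of change from that swab could hide the effect or reverse its sign.

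The second matter is efficiency. A baseline swab is already collected from everyone, but the plan does not use it to sharpen the arm comparison.

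**Working it through.** **Inputs.** The documents give no figure for flora, so there is none to reproduce. They state no scale, SD or correlation. The 150 evaluable subjects in Section 10 are for infection, not swabs; I use 75 per arm only as a convenient size. The effects, the correlation r between swabs, unit SDs and a two-sided 5% level are all assumptions.

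**1. What each choice of 'pre' estimates.** Let e1 be the arm effect at the day-of-surgery swab and e2 the effect at the follow-up swab.

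- Arm comparison at follow-up, unadjusted or adjusted for screening: estimates e2.
- Arm comparison of change from day of surgery: estimates e2 − e1.

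Take e1 = 0.5 SD and r = 0.3. The standard error of the change contrast is √[(2/75) × 2(1 − 0.3)] = 0.193 SD.

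| e2 (SD) | Change from day of surgery estimates (SD; positive favours CHG) |
|---|---|
| 0.50 | 0.00 |
| 0.25 | −0.25 (wrong direction) |
| 0.75 | 0.25 |

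In the first row, simulation gives about a 2% chance of a significant result favouring CHG, against 89% for the screening-adjusted comparison. In the second, the chance of a significant result against CHG is Φ(0.25/0.193 − 1.96) ≈ 25%. The identity e2 − e1 does not depend on the assumed values; the percentages do.

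**2. What adjustment gains over the planned arm comparison.** Relative to follow-up only, the large-sample variance is 1 − r² with the screening covariate. For change from screening it is 1 + k² − 2rk, where k is the ratio of screening SD to follow-up SD. The second minus the first is (k − r)², which is never negative, so adjustment is never less precise than a change score in large samples.

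Unadjusted power for 0.5 SD is Φ(0.5/√(2/75) − 1.96) = Φ(3.062 − 1.960) ≈ 86.5%, or 86.0% using the t distribution. For the adjusted comparison, 3.062 is divided by √(1 − r²):

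| r | Variance, adjusted | Variance, change from screening (k = 1) | Power, adjusted |
|---|---|---|---|
| 0.2 | 0.96 | 1.60 | about 87% |
| 0.3 | 0.91 | 1.40 | about 89% |
| 0.5 | 0.75 | 1.00 | about 94% |

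The gain is about 1, 3 and 8 percentage points. At r = 0 the cost is a variance factor of (150 − 3)/(150 − 4) = 1.007. For a growth/no-growth result, simulation of a baseline-standardised risk difference gives similar factors: 0.97, 0.92 and 0.75 at phi = 0.2, 0.3 and 0.5.

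**3. What happens if the baseline is not clean.** Suppose controls were swabbed after soap and this lowered their screening value by s. The adjusted estimate then shifts by r × s towards CHG. With s = 0.3 SD and r = 0.3 the shift is 0.09 SD. The standard error is √[(2/75) × 0.91] = 0.156, so type I error is about Φ(0.578 − 1.96) + Φ(−0.578 − 1.96) = 0.083 + 0.006, roughly 8 to 9%. The unadjusted comparison stays at 5%.

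**4. Number of comparison times.** Three swabs each tested at 5% give at most 1 − 0.95³ = 14.3% if independent. One named swab keeps this at 5%.

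**5. Timing of the last swab.** Section 4 says "Additional evaluations will take place at the 30 day (+/- 7 days) post-op visit", which is days 23 to 37. The schema puts the last culture at 6 weeks ± 1 week, days 35 to 49. The windows share only days 35 to 37.

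**The case against.** The strongest reply is that the plan already contains a sound analysis. Section 3 compares the arms at each listed swab, and that randomized contrast estimates e2 without bias, with about 86% power under the inputs above. This stands, and it limits the point to an efficiency gain and a clarification. A reader might infer from the 2% against 89% contrast that the plan would probably miss a real effect. The documents do not support that: it would require both that 'pre' means day of surgery and that change from it replaces the planned arm comparison.

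The objectives also list day of surgery among the comparison times, which leaves screening as the natural baseline. That is a fair hint, but no section says so.

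A reader might also infer from the schema that controls were washed before their screening swab. The tick does not show this. The row for the cloths carries the same screening tick, yet its footnote explains that supplies are handed over then and applied later. That footnote does not cover the control row, so the order for controls is simply unstated.

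Finally, flora has no stated hypothesis or power, and may be recorded as organism types, for which neither suggested model fits directly. This too stands: the measure must be defined before the model is chosen.

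**Conclusion.** The point holds as a minor improvement. The plan does not say which preoperative swab is 'pre' and does not use the screening swab as a covariate. Change from the day-of-surgery swab estimates e2 − e1 and should be ruled out for the arm comparison, but nothing shows that it is the intended analysis.

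The realistic benefit is that of adjusting the planned comparison: negligible at a correlation of 0.2 or less, modest at 0.3, and useful at 0.5. All of this rests on assumed correlations and a quantitative or binary measure. It also needs a screening swab taken before study cleansing in both arms. The documents describe the screening site as close to the intended incision line and the later site as the incision itself; a real difference between them could lower the correlation and shrink the gain. Nothing here bears on the infection sample size.

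**What to change.** In Section 4:

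1. Name the screening swab as the flora baseline.
2. Confirm that it is taken before any study cleansing in both arms, including soap and water in controls, and at the same site as the later swabs.
3. Define the flora measure and name one follow-up swab for the main comparison, with the others secondary.
4. Compare the randomized arms at that swab with the screening value as covariate: ANCOVA on log count if quantitative, or a baseline-standardised risk difference if growth/no growth.
5. Keep within-person changes descriptive. The day-of-surgery swab may be an outcome, but not the 'pre' value for the arm comparison.

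If the order in controls cannot be confirmed, use the unadjusted comparison, which that order does not affect. Reconcile the 30-day timing of the last swab in Sections 3 and 4 with the 6-week visit in the schema.

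The cost is a few lines of text, settled before flora data are analysed. No new swab or visit is needed.

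### Does the sample size of 150 with 80% power in Section 10 contain an arithmetic error that puts the trial at risk?

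*Combined protocol and SAP*

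**What the plan says.** The sample size rests on two statements in Section 10, which read the same in both copies of the protocol. The first gives the control rate: "Prior data indicate the rate of infection in the control group (those with risk factors, including superficial SSI) is 0.5". The second gives the size and power: "then just 150 evaluable subjects are needed to detect a 50% or greater reduction, with 80% power". The section opens with "We are planning a study of independent cases and controls with 1 control(s) per case".

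Elsewhere, Section 6 states "170 patients will be enrolled", Section 4 states that "patients will be randomized to one of 2 arms in 1:1 through a block randomization table", and the end of Section 1 says "This study proposes a randomized, controlled trial of neuro-spine patients".

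Alpha, sidedness, the test, the scale of the reduction, and whether 150 is a total or a per-arm number are not given.

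**The concern.** A power statement should be reproducible from its inputs. With the usual conventions this one is not: the common formulas for 0.5 against 0.25 at the 0.05 level all give totals clearly below 150, so 150 and 80% do not seem to belong together.

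The opening sentence of Section 10 adds to the doubt. It uses case-control language in a randomized trial, and case-control sample sizes are often worked out on the odds-ratio scale. If the 50% meant a halving of the odds, the treated rate would be 0.333 rather than 0.25, and 150 subjects in total would fall far short of 80% power. What would be at stake is whether the only sample-size figure with a rationale hides a seriously underpowered trial.

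**Working it through.** **Inputs.** Control rate 0.5, a 50% reduction, 80% power and 150 evaluable come from Section 10; 1:1 allocation from Section 4; 170 enrolled from Section 6. Two-sided alpha 0.05 is my assumption. The number 150 is taken as a total (75 per arm), because 170 enrolled cannot contain 150 per arm. The difference 170 − 150 = 20 leaves 20/170 = 11.8% for non-evaluable subjects.

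**Step 1: the natural reading, 0.5 against 0.25.** With z = 1.960 and 0.842, d = 0.25, mean rate 0.375, and p1(1−p1) + p2(1−p2) = 0.25 + 0.1875 = 0.4375:

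- Unpooled: n = (1.960 + 0.842)² × 0.4375 / 0.0625 = 54.9, so 55 per arm, 110 in total.
- Pooled: n = [1.960 × √(2 × 0.375 × 0.625) + 0.842 × √0.4375]² / 0.0625 = 57.7, so 58 per arm, 116 in total.
- Continuity-corrected: n = (57.7/4) × [1 + √(1 + 4/(57.7 × 0.25))]² = 65.4, so 66 per arm, 132 in total.
- Fisher's exact test, by enumeration: 64 per arm (power 0.802; 63 gives 0.794), 128 in total.

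One-sided at 0.05 the totals are 88 to 108. None of these is 150.

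**Step 2: power at 75 per arm.** (0.25 × √75 − 1.960 × √0.46875) / √0.4375 = 1.24, which gives 89.3%. Fisher gives 86.3%. One-sided, the values are 94.2% and 92.4%. The excess over the two-sided requirement is 150 − 132 = 18 to 150 − 110 = 40 subjects, or 14% to 36%.

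**Step 3: can ordinary inputs give 150 with 80%?**

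- The control rate is printed to one decimal, and 0.46 rounds to 0.5. For 0.46 against 0.23 at two-sided 0.05, the mean rate is 0.345, the variance sum is 0.2484 + 0.1771 = 0.4255, and d² = 0.0529. The pooled formula gives 65.9 and the continuity-corrected one 74.3, so 75 per arm and exactly 150 in total. Fisher power at 75 per arm is 80.7%.
- For 0.5 against 0.25 with two-sided alpha 0.02 (or one-sided 0.01), the pooled formula gives 74 per arm, 148 in total.

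The documents show neither route to be the one used. Both show that the stated pair is attainable.

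**Step 4: the odds-ratio reading.** The control odds are 0.5/0.5 = 1. Halved, they are 0.5, so the treated rate is 0.5/1.5 = 0.333. At two-sided 0.05 this needs 134 (unpooled), 137 (pooled), 147 (Fisher) or 148 (corrected) per arm, which is 268 to 296 in total. Power at 75 per arm is 54.5% (Fisher 50.2%), and 66.7% one-sided (Fisher 61.6%). The number 150 comes out only as a per-arm figure, which needs 300 evaluable subjects against 170 enrolled.

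**The case for a change.** The strongest case for acting is that a power statement without alpha, test or scale cannot be verified. On the plain reading at 0.05 the text calls 150 necessary for 80% when 132 or fewer would do, and the case-control sentence makes a halving of the odds conceivable. The remedy would be only a sentence or two.

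Part of this stands. The inputs are missing, and the opening sentence of Section 10 does not describe this trial. The arithmetic in Steps 1, 2 and 4 is also correct for its stated inputs.

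Two parts do not stand. First, a figure cannot be called miscalculated when the reader has to supply its alpha and test, and when an unrounded control rate of 0.46 or a stricter alpha reproduces it or nearly so. Second, the 54% scenario joins an effect measure that no section mentions to a total which that measure does not produce. Section 10 refers to an infection rate and then to a reduction, the hypothesis in Section 2 concerns decreasing rates, and the precedent in Section 1 is a decrease in infections of up to 50%. Against that, one sentence that is most simply read as loose wording for two equal independent groups carries little weight.

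**Conclusion.** No change follows. Section 10 leaves out details that a statistician would supply in the ordinary way: two independent proportions, 1:1, a relative reduction, 150 in total. On that reading, at an assumed alpha of 0.05, the trial has more power than claimed, about 89% two-sided (86% by Fisher), and 150 exceeds every requirement computed. If the control rate was rounded up from 0.46, or alpha was 0.02, the stated 80% is about right. Under none of these readings does a trial run as written fall materially short of its stated power, so writing the inputs down would alter neither the enrolment of 170 nor the comparison of the two arms. The cases-and-controls sentence is a wording slip, since Sections 1 and 4 establish the randomized design.

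The conclusion rests on three assumptions: 150 is a total, the reduction is in the rate, and the control rate is near 0.5. The first two are well supported by the text. The third is taken as given here. Section 1 says "Vanderbilt University Medical Center SSI rate is 7" percent, a figure not restricted to patients with risk factors. Whether 0.5 is plausible beside it is a different matter, and nothing here endorses that rate.
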